9.2.1. Inclusion criteria

Patients must meet all of the following inclusion criteria to be eligible for inclusion in the study:

1. ≥ 18 year old female
2. HR+/HER2- breast cancer diagnosis with confirmed metastatic or advanced disease
3. Diagnosed with ABC/MBC between 01 January 2016 and 01 July 2021
4. Treatment with CDK4/6 inhibitor

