2. LIST OF ABBREVIATIONS

Abbreviation	Definition
ABC/MBC	Advanced/metastatic breast cancer
AE	Adverse events
AEM	Adverse event monitoring
AI	Aromatase Inhibitor
CDK	Cyclin-dependent kinase
CDK4/6	Cyclin-dependent kinase 4 and 6
CI	Confidence Interval
COVID-19	COronaVIrus Disease 2019
CSV	Comma separated values
ECOG	Eastern Cooperative Oncology Group
EHR	Electronic health record
EMR	Electronic Medical Record
ER	Estrogen Receptor
GPP	Guidelines for Good Pharmacoepidemiology Practices
HER2	Human epidermal growth factor receptor 2
HR	Hormone receptor
IEC	Independent ethics committee
IRB	Institutional review board
IRIS	Ibrance Real world Insights Study

PFIZER CONFIDENTIAL

[figure not shown]
ISPE	International Society for Pharmacoepidemiology
LHRH	luteinizing hormone-releasing hormone
NIS	Non-interventional study
NLP	Natural language processing
NSAI	Non steroidal aromatase inhibitor
OS	Overall survival
PFS	Progression Free Survival
PR	Progesterone receptor
RCT	Randomized clinical trial
SABCS	San Antonio Breast Cancer Symposium
SD	Standard deviation
TTNT1	Length of treatment for the first line
TTNT2	Length of treatment for the second line
TTC	Time from date of ABC/MBC diagnosis to starting chemotherapy
SAP	Statistical analysis plan
VM	Virtual machine
YRR	Your reporting responsibility

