9.2. Setting

The study period will extend from 01 January 2016 to 01 October 2021 (Figure 1). All female patients who are ≥ 18 years of age and are diagnosed with HR+/HER2- ABC/MBC and received a CDK4/6 inhibitor at Sinai Health during the study period will be included in the study. It is estimated that there will be approximately 300 diagnoses of ABC/MBC within the study period at Sinai Health, of which approximately 180 will be HR+/HER2-. Follow-up data from EHRs will be included up to the extent that they are available within the study period. Pre-index data (stage at initial breast cancer diagnosis, treatment being received at ABC/MBC diagnosis) may be extracted from EHRs up to 12 months before the index date.

[figure not shown]

Figure 1. Study Design Flow Chart

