9.3. Variables

Table 1. List of study variables to be extracted (where feasible)

Variable	Role	Data source(s)	Operational definition
Patient demographics	Baseline characteristic, potential confounder, sub-group identifier	Patient EHR	
• Date of birth• Sex• Date of death
Clinical characteristics	Baseline characteristic, potential confounder, sub-group identifier	Patient EHR	
• Date of ABC/MBC diagnosis• Age at ABC/MBC diagnosis (years)• ECOG performance score at index date (0, 1, 2, 3, 4)• ESAS• Date of last follow-up• Organ level metastatic sites (bone, brain, lungs, liver; number of sites)• Tumour stage at initial breast cancer diagnosis (I, II, III, IV, Unknown)• Tumour grade• Tumour histology• ER and PR receptor status (Positive, Negative, Unknown)• HER2 status (Positive, Negative, Unknown)• Concomitant LHRH agonists
Comorbidities	Baseline characteristic, potential confounder, sub-group identifier	Patient EHR	
• Atrial fibrillation• Hypertension• Coronary Artery Disease/Myocardial infarction/Angina• Diabetes Mellitus• Stroke
Treatments	Exposure	Patient EHR	
• Systemic Therapies (therapy start and stop date including combination therapies, and line of therapy)• Surgeries• Radiation Treatment
Clinical outcomes	Outcome	Patient EHR	
• TTNT1• TTNT2• TTC• Overall Survival (landmark 3y)

ECOG, Eastern Cooperative Oncology Group; EHR, Electronic Health Record; ER, Estrogen Receptor; ESAS, Edmonton Symptom Assessment System; HER2, Human Epidermal Receptor Growth Factor 2; LHRH, Luteinizing Hormone-Releasing Hormone; PR, Progesterone Receptor; TTC, time from date of ABC/MBC to starting chemotherapy; TTNT1, length of treatment for the first line; TTNT2, length of treatment for the second line

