5.5 ENDPOINTS

Variable	Role	Data source(s)	Operational definition
Patient demographics	Baseline characteristic, potential confounder, subgroup identifier	Patient EHR	
• Date of birth• Sex• Date of death
Clinical characteristics	Baseline characteristic, potential confounder, subgroup identifier	Patient EHR	
• Date of ABC/MBC diagnosis• Age at ABC/MBC diagnosis (years)• ECOG performance score at index date (0, 1, 2, 3, 4)• ESAS• Date of last follow-up• Organ level metastatic sites (bone, brain, lungs, liver; number of sites)• Tumour stage at initial breast cancer diagnosis (I, II, III, IV, Unknown)• Tumour grade

PFIZER CONFIDENTIAL

			
 • Tumour histology • ER and PR receptor status (Positive, Negative, Unknown) • HER2 status (Positive, Negative, Unknown) • Concomitant LHRH agonists
Comorbidities	Baseline characteristic, potential confounder, subgroup identifier	Patient EHR	
 • Atrial fibrillation • Hypertension • Coronary Artery Disease/Myocardial infarction/Angina • Diabetes Mellitus • Stroke
Treatments	Exposure	Patient EHR	
 • Systemic Therapies (therapy start and stop date including combination therapies, and line of therapy) • Surgeries • Radiation Treatment
Clinical outcomes	Outcome	Patient EHR	
 • TTNT1 • TTNT2 • TTC • Overall Survival (landmark 3y)

ECOG, Eastern Cooperative Oncology Group; EHR, Electronic Health Record; ER, Estrogen Receptor; ESAS, Edmonton Symptom Assessment System; HER2, Human Epidermal Receptor Growth Factor 2; LHRH, Luteinizing Hormone-Releasing Hormone; PR, Progesterone Receptor; TTC, time from date of ABC/MBC diagnosis to starting chemotherapy; TTNT1, length of treatment for the first line; TTNT2, length of treatment for the second line

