7 STATISTICAL METHODOLOGY AND STATISTICAL ANALYSES

7.1 STATISTICAL METHODS

The following analyses are expected to be conducted in R.

Analyses for continuous Data

Continuous variables will be described by the number of patients with valid/non-missing observations using mean, standard deviation (SD), quantiles (Q1, median, Q3), minimum and maximum.

Analyses for Categorical Data

Categorical variables will be described by frequencies and related percentages.

Analyses for time to event end points.

Time to event variables will be analyzed using Kaplan-Meier curves (TTNT1, TTNT2, TTC, OS). Numbers at risk and cumulative incidence will be reported for each curve.

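### Cohort entry depends on a CDK4/6 inhibitor started at any time in the study period, but time to chemotherapy (and possibly OS) is counted from diagnosis, so ordinary Kaplan-Meier curves contain survival time guaranteed by selection

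*Protocol*

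**What the plan says.** **Entry.** The fourth inclusion criterion in Protocol 9.2.1, repeated in SAP 4.1, is "Treatment with CDK4/6 inhibitor". It gives no line of therapy and no maximum gap from diagnosis. The only time limit is in Protocol 9.2: patients who "received a CDK4/6 inhibitor at Sinai Health during the study period will be included in the study", and that period ends on 01 October 2021. The diagnosis window is "Diagnosed with ABC/MBC between 01 January 2016 and 01 July 2021".

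**Time origin.** Protocol Section 2 defines TTC as "Time from date of ABC/MBC diagnosis to starting chemotherapy", and the footnote in SAP 5.5 agrees: "TTC, time from date of ABC/MBC diagnosis to starting chemotherapy". For OS, Protocol Table 1 gives only "Overall Survival (landmark 3y" and no readable start date. Protocol 9.2 allows pre-index data "up to 12 months before the index date", and Protocol 9.4 counts the same 12 months back from ABC/MBC diagnosis. This suggests, but does not state, that the index date is the diagnosis.

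**Estimator.** SAP 7.1 states "Time to event variables will be analyzed using Kaplan-Meier curves (TTNT1, TTNT2, TTC, OS", and Protocol 9.7 calls the chart unadjusted. No readable text mentions delayed entry, a landmark at CDK4/6 inhibitor start, or a CDK4/6 inhibitor time origin.

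**Status.** SAP 7.2.2 lists treatment duration, TTC and OS as exploratory, analysed in all patients.

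**The concern.** Membership of the cohort is decided by something that happens after the clock starts. A woman who died, or moved to chemotherapy and never received a CDK4/6 inhibitor, is not in the data. A woman whose CDK4/6 inhibitor began 18 months after diagnosis is counted as at risk of death from day 0, although a death before month 18 would have kept her out. An ordinary Kaplan-Meier curve treats that guaranteed time as observed follow-up.

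For TTC the problem takes a different form. Chemotherapy before the CDK4/6 inhibitor is not an exclusion (Protocol 9.2.2), so some events precede the exposure that made the patient eligible. They are seen only in women who survived and then received a CDK4/6 inhibitor.

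What is at stake is the meaning of the 3-year OS figure (if timed from diagnosis) and of the TTC median and cumulative incidence. A reader would take them as prognosis from diagnosis. They mix that with the selection of women who lived long enough to receive the drug class.

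**Working it through.** The plan gives no figure to reproduce. The check is one of logic, followed by illustrations with stated assumptions. In all of them CDK4/6 inhibitors have no effect on survival, and the truth is survival of everyone diagnosed.

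**1. Does the plan expect lags above zero?** Yes. SAP 7.2 defines a pre-CDK subgroup that was diagnosed and started systemic therapy in January to May 2016, before palbociclib was introduced in Canada. SAP 4.3 draws it from the full analysis set, where everyone has received a CDK4/6 inhibitor. These women can qualify only through a later CDK4/6 inhibitor.

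**2. Same lag L for all, exponential survival.** Ordinary Kaplan-Meier at 36 months then estimates S(36)/S(L) = exp(-h(36 - L)).
- Low anchor (22% 5-year stage IV survival, Protocol 7): h = -ln(0.22)/60 = 0.0252 per month and true S(36) = 40.3%. The estimate is 43.5% for L = 3, 46.9% for L = 6 and 54.6% for L = 12 months.
- High anchor (95.6% 12-month survival with palbociclib + AI, Protocol 7): h = -ln(0.956)/12 = 0.00375 and true S(36) = 87.4%. The estimate is 91.4% for L = 12.

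**3. Mixed lags, unrelated to prognosis.** Diagnosis is uniform over 66 months with the cut at month 69, so potential follow-up is 3 to 69 months. A patient is included only if the CDK4/6 inhibitor starts before death and before the cut.
- Low anchor (true 40.3%): 40.9% if all start within 1.5 months; 43.1% with 25% late (mean lag 12 months); 45.1% with 50% late (mean 12); 46.5% with 50% late (mean 24).
- High anchor (true 87.4%): 87.8% to 89.6%.
- Median survival 30 months (true 43.5%): 51.6%, 48.9% and 46.7% when 40%, 60% and 80% start within 2 months and the rest after a median of 12 more months. Median 42 months (true 55.2%): 62.5%, 60.1% and 58.2%.

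The overstatement is about 0.5 to 8 points. Delayed entry at CDK4/6 inhibitor start is within about 0.6 point of the truth in every case here.

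**4. Late starters begin at progression.** Same windows, with 40%, 60% or 80% starting within 2 months and the rest at progression. Median time to progression is 14 or 24 months; the monthly death hazard is 0.003 to 0.01 before and 0.03 or 0.04 after progression.
- Over 30 such scenarios, ordinary Kaplan-Meier missed 3-year OS by -4.8 to +1.7 points. Delayed entry understated it by 1.5 to 13.8 points.
- Lowest case (24 months, 0.003 then 0.04, 40% early): true 60.4%, ordinary 55.7%, delayed entry 46.6%.
- Highest case (14 months, 0.01 then 0.03, 40% early): true 49.0%, ordinary 50.7%, delayed entry 42.9%.

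**5. TTC.** The 24-month chemotherapy-free share is 50% by assumption, deaths are censored, survival is at the low anchor, and 25% or 50% start late (mean 12 months). Ordinary Kaplan-Meier gives 51.7% or 54.3% if chemotherapy rules out a later CDK4/6 inhibitor, 50.6% or 49.9% if it makes no difference, and 49.2% or 48.6% if it doubles the rate of starting one. The sign depends on an unknown.

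**6. Which displays are most exposed.** SAP Figures 8 and 9 split TTC and OS by type of treatment. Strata whose first line was not a CDK4/6 inhibitor carry most of the guaranteed time. Figure 17 compares OS by diagnosis in the year before and the first year of COVID-19. By 01 October 2021 the first group has had about 19 to 31 months in which to qualify and the second about 7 to 19, so the bias can differ between the two curves.

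**7. Precision.** The amendment logs expect under 30% of 180 patients, that is, fewer than 0.30 x 180 = 54. The binomial standard error of a 40% estimate with 54 patients is sqrt(0.4 x 0.6/54) = 6.7 points.

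**The case against.** - *The outcomes need not look too good.* A reader might infer from the guaranteed time that OS and TTC must be biased favourably. The documents do not support that. A later-line CDK4/6 inhibitor may well follow failure of an earlier line, and the lag then carries prognostic information. Step 4 shows the OS error can shrink or reverse, and step 5 shows the TTC sign is open. This stands.
- *Delayed entry is not a safe repair.* A reader might take left-truncated Kaplan-Meier as the obvious correction. It needs the lag to be independent of survival, which nothing in the documents supports, and step 4 shows it can do worse than the ordinary curve. With fewer than 54 patients the early risk sets would also be small. This stands.
- *The OS origin is not readable.* SAP 5.1 and much of the time-to-event text are redacted. Protocol Table 1 refers separately to age at diagnosis and ECOG at the index date, so the two dates may differ. The OS part must stay conditional. The TTC origin is explicit.
- *The origin of TTC was chosen deliberately.* Both amendment logs say it was moved from CDK4/6 inhibitor start to diagnosis on clinical expert advice. That is a reason to keep it, but it does not remove the selection.
- *The study is descriptive and already cautious.* There is no inference, the endpoints are exploratory, and no comparison with the survival figures in Protocol 7 is planned. Protocol 9.9 names selection and channelling bias, though not this mechanism, and presents the eligibility criteria as limiting selection bias. This lowers the severity. A descriptive label does not correct the estimate, and a standard error does not reveal the bias.

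**Conclusion.** The design problem holds on the readable text. Eligibility rests on an exposure that may come long after diagnosis, TTC runs from diagnosis, and the estimator makes no allowance. Ordinary Kaplan-Meier from diagnosis therefore does not estimate time to chemotherapy, or OS if it shares that origin, for a definable population.

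The size depends on the diagnosis-to-CDK4/6 inhibitor lag, which the documents do not give. With a lag unrelated to prognosis, 3-year OS is overstated by about 0.5 to 8 points under the mixed-lag assumptions. With later-line use triggered by progression, the illustrated error is -4.8 to +1.7 points. For TTC it runs from about +4 to -1.5 points. It is near zero if almost all patients start at diagnosis.

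A reader might also conclude that the study's main result is compromised. It is not: the primary objective describes treatment patterns and is not a time-to-event estimate. The point should be fixed but is not critical.

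**What to change.** In SAP 7.1 and 7.2:
1. Keep TTC from diagnosis as defined. Add OS and time-to-chemotherapy curves with time zero at first CDK4/6 inhibitor start, by line of CDK4/6 inhibitor where numbers allow. Base any effectiveness statement on these. They remove the guaranteed time without the independence assumption.
2. Count patients with chemotherapy before the first CDK4/6 inhibitor separately and leave them out of the added chemotherapy curve.
3. Report the distribution of the lag from diagnosis to first CDK4/6 inhibitor.
4. Show delayed-entry Kaplan-Meier from diagnosis only as a sensitivity analysis, stating that it assumes a lag independent of survival and that early risk sets will be small.

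In Protocol 9.9, name this selection. Make sure the OS time origin is stated, if the redacted text does not already do so.

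Cost: SAP wording and one extra set of curves. Therapy start dates are already in Protocol Table 1, so no new data are needed. The added chemotherapy curve uses the origin that the amendment replaced, so it should be labelled a supplement to TTC and not a substitute. Strata by line will be thin with fewer than 54 patients.

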9.2.2. Exclusion criteria

Patients meeting any of the following will not be included in the study:

1. Patient does not have ABC/MBC

PFIZER CONFIDENTIAL

2. Patient has indicated HR- or HER2+ status
3. Patient received a CDK4/6i as part of a clinical trial

9.3. Variables

Table 1. List of study variables to be extracted (where feasible)

Variable	Role	Data source(s)	Operational definition
Patient demographics	Baseline characteristic, potential confounder, sub-group identifier	Patient EHR	
• Date of birth• Sex• Date of death
Clinical characteristics	Baseline characteristic, potential confounder, sub-group identifier	Patient EHR	
• Date of ABC/MBC diagnosis• Age at ABC/MBC diagnosis (years)• ECOG performance score at index date (0, 1, 2, 3, 4)• ESAS• Date of last follow-up• Organ level metastatic sites (bone, brain, lungs, liver; number of sites)• Tumour stage at initial breast cancer diagnosis (I, II, III, IV, Unknown)• Tumour grade• Tumour histology• ER and PR receptor status (Positive, Negative, Unknown)• HER2 status (Positive, Negative, Unknown)• Concomitant LHRH agonists
Comorbidities	Baseline characteristic, potential confounder, sub-group identifier	Patient EHR	
• Atrial fibrillation• Hypertension• Coronary Artery Disease/Myocardial infarction/Angina• Diabetes Mellitus• Stroke
Treatments	Exposure	Patient EHR	
• Systemic Therapies (therapy start and stop date including combination therapies, and line of therapy)• Surgeries• Radiation Treatment
Clinical outcomes	Outcome	Patient EHR	
• TTNT1• TTNT2• TTC• Overall Survival (landmark 3y)

ECOG, Eastern Cooperative Oncology Group; EHR, Electronic Health Record; ER, Estrogen Receptor; ESAS, Edmonton Symptom Assessment System; HER2, Human Epidermal Receptor Growth Factor 2; LHRH, Luteinizing Hormone-Releasing Hormone; PR, Progesterone Receptor; TTC, time from date of ABC/MBC to starting chemotherapy; TTNT1, length of treatment for the first line; TTNT2, length of treatment for the second line

9.4. Data sources

Patients will be selected with dates of diagnosis of HR+/HER2- ABC/MBC between 01 January 2016 and 01 July 2021. Study data will be extracted from Sinai Health EHRs up to 12 months before ABC/MBC diagnosis until the end of the study period (01 October 2021, [Figure 1](#)).

9.5. Study size

All female patients who are ≥ 18 years of age and are diagnosed with HR+/HER2- ABC/MBC at Sinai Health during the study period will be included in the study. It is estimated that there will be approximately 300 diagnoses of ABC/MBC within the study period at Sinai Health, of which approximately 180 will be HR+/HER2-. All analyses are descriptive in nature and so sample size calculations are not applicable.

9.6. Data management

At Sinai Health's direction, DARWENT™ shall run in a secure environment that meets Sinai Health's IT and privacy requirements. DARWENT™ engine structures data optionally on a compute cluster, using models supported/reinforced, if needed, through additional training on Sinai Health data. DARWENT™ engine outputs patient-level data which can be structured as a Comma separated values (CSV) on the VM.

Data extracted from Sinai Health EHRs and curated by DARWENT™ will be retained by Sinai Health for research purposes in a row and column dataset in the file-type/format of their choosing. Sinai Health retains all ownership and rights to the data.

Pentavere will provide Pfizer with aggregate data following Sinai Health's approval. Aggregate data will be sent to Pfizer directly from Sinai Health by Pentavere when directed to do so by Sinai Health, and, if requested, a secured share drive can be created for data storage and transfer. Pentavere will comply with Sinai Health procedures regarding content, archiving, records management of process documents, and electronic transfer of these aggregate data.

9.6.1. Case report forms/Data collection tools/Electronic data record

As described above, data extracted from Sinai Health EHRs and curated by DARWENT™ compliant process will result in de-identified aggregated patient data.

9.6.2. Record retention

To enable evaluations and/or inspections/audits from regulatory authorities or Pfizer, the third party responsible (Sinai Health/Pentavere) agrees to keep records, including the identity of all participating patients, safety reporting forms, source documents, detailed records of treatment disposition, and adequate documentation of relevant correspondence (e.g., letters, meeting

minutes, and telephone call reports). The records should be retained by the investigator according to local regulations or as specified in the clinical study agreement (CSA), whichever is longer. The investigator must ensure that the records continue to be stored securely for so long as they are retained.

If the investigator becomes unable for any reason to continue to retain study records for the required period (e.g., retirement, relocation), Pfizer should be prospectively notified. The study records must be transferred to a designee acceptable to Pfizer, such as another investigator, another institution, or to an independent third party arranged by Pfizer.

Study records must be kept for a minimum of 25 years after completion or discontinuation of the study, as required by Health Canada's regulations.

[figure not shown]
The investigator must obtain Pfizer's written permission before disposing of any records, even if retention requirements have been met.

9.7. Data analysis

Detailed methodology for summary and statistical analyses of data collected in this study will be documented in a statistical analysis plan (SAP), which will be dated, filed and maintained by the sponsor. The SAP may modify the plans outlined in the protocol; any major modifications of primary endpoint definitions or their analyses would be reflected in a protocol amendment. Statistical analyses will be performed by PPD. The data will be analyzed using R (version and packages will be detailed in final SAP).

Descriptive analyses will be performed to summarize patients' baseline characteristics and outcomes of interest across the study cohort. Continuous variables will be described by the number of patients with valid/non-missing observations using mean, standard deviation (SD), minimum, maximum and quantiles (Q1, median, Q3). Categorical variables will be described by frequencies and related percentages. Number of missing observations will be reported for all variables. Time to event will be described using unadjusted Kaplan-Meier chart that will visually estimate the distribution of times to some events (i.e. progression), and will take into account those patients for which the event has not as yet occurred. Numbers at risk, cumulative incidence and survival medians will be reported for each curve. Endpoint definitions and how patients are censored for each endpoint will be further described in the SAP. Visualizations may be used to further describe treatment patterns, patient journeys, and other outcomes of interests if appropriate. The above planned data analyses are descriptive in nature and all subject to modification based on sample size and final data specifications. No inferential statistical analyses will be conducted.

PFIZER CONFIDENTIAL

Missing data will be excluded on a case by case basis and will not be imputed. This will mean that each table will not necessarily be based on the same number of patients.

CCI

